#### ***Post-treatment adverse events***

- All post-treatment AEs by primary SOC and PT, sorted by the internationally agreed SOC order and decreasing incidence of PTs (in the alirocumab group) within each SOC;
- All post-treatment SAEs by primary SOC and PT, sorted by the sorting order defined above.

#### ***Subgroup of patients with two consecutive LDL-C <25 mg/dL (<0.65 mmol/L)***

If applicable, similar summaries of TEAEs as those described above will be provided on the safety subgroup population of patients with two consecutive results of LDL-C <25 mg/dL (as defined in [Section 4.8](#)) in both treatment groups. Only TEAEs for which it will be confirmed or unclear that they occurred, worsened or became serious on the day or after the day the first level of LDL-C <25 mg/dL was observed will be considered in this summary. These analyses will be restricted to the respective treatment periods. The summaries of the subgroup of patients with two-consecutive LDL-C values <25 mg/dL in the double-blind treatment period will only consider TEAEs with a start date within the double-blind treatment period; summaries of the subgroup of patients with two-consecutive LDL-C values <25 mg/dL in the open-label period will only consider TEAEs with a start date within the open-label treatment period.

##### **5.7.1.1. Patient Deaths**

The following summaries of deaths will be generated.

- Number (%) of patients who died by study period (TEAE and post-treatment in both the double-blind and open-label periods);
- Deaths in nonrandomized patients or randomized but not treated patients;
- TEAEs leading to death (death as an outcome on the AE CRF page, as reported by the Investigator) by (at least) SOC (sorted by internationally agreed order), and PT (sorted by decreasing frequency, showing the number (n) and percentage (%) of patients) for both the double-blind and open-label study periods.

#### ***Analysis of Adverse Event in the Open-Label Period***

For open-label period, summary of adverse events as described for the double-blind period will be used.

### 5.7.2. Analysis of Clinical Laboratory Variables

Clinical laboratory parameter actual values (quantitative) and change from baseline values will be descriptively summarized at baseline and each post-baseline visit (collected up to the day of last dose of study treatment +21 days) by at least patient number, mean, median, Q1, Q3, SD, minimum and maximum for each treatment group. Additionally, laboratory parameter measures for last on-treatment values and worst on-treatment values will be summarized in a similar manner. Clinical laboratory parameters mean changes from baseline, with the corresponding SE, can be plotted at each visit by treatment group, in the case results warrant further investigation. These parameters will be presented by the biological functions defined in [Section 4.7.2](#). For glucose, only fasting samples will be included in the summaries.

Individual patient laboratory parameter measurements will be additionally evaluated by PCSA criteria, specifically identifying patients with at least one post-baseline measurement that meets the PCSA criteria within the TEAE period. The following additional project specific PCSA criteria will also be evaluated during the TEAE period:

- Patients with a hemoglobin decrease from baseline  $\geq 15$  g/L.
- Patients meeting the ALT increase defined in [Section 4.7.1.2](#).
- Glucose (quantitative summary and PCSA) will also be analyzed, overall and according to the diabetic status at baseline.

Patients meeting the PCSA criteria at least once will be summarized by patient count (and percent) for a post-baseline PCSA measurement while accounting for the baseline PCSA status (PCSA normal/missing; PCSA abnormal), for each treatment group. For the appendix, this laboratory parameter PCSA table will be reproduced with patients meeting the PCSA criteria at least once during the TEAE period regardless of baseline PCSA status. These laboratory parameters will be presented by the biological functions defined in [Section 4.7.2](#). Patient listings of laboratory measurements that meet PCSA criteria will be provided for the report appendix. For those laboratory parameters that don't have an associated PCSA criteria, similar summary tables can be provided based on measurements outside the central laboratory normal ranges, if applicable.

#### ***Hepatitis C antibody***

The number and percentage of patients with a post-baseline seroconversion for hepatitis C test will be provided by treatment group in post-baseline (including the TEAE and post TEAE periods) as well as in the TEAE period alone. Post-baseline seroconversion is defined for patients with a negative baseline status who had either a “positive RNA” or a “confirmed positive antibody with negative RNA” post-baseline status as defined in the table below. Other situations require case by case evaluation and will be described individually if relevant.

The status as regards hepatitis C virus for a patient will be defined as follows for all evaluations (baseline and post-baseline).

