- Hepatitis B surface antigen and/or Hepatitis C antibody (associated with a positive HCV RNA polymerase chain reaction) at the screening visit
- Positive serum beta-human chorionic gonadotropin (hCG) or urine pregnancy test in women of childbearing potential
- Estimated glomerular filtration rate (eGFR)  $<30$  mL/min/1.73 m^2 (calculated by central lab)
- Alanine aminotransferase (ALT) or aspartate aminotransferase (AST)  $>3$  x upper limit of normal (ULN) (1 repeat lab is allowed)
- Unexplained serum creatine phosphokinase CPK  $>5$  x ULN (1 repeat lab is allowed)

19. Known hypersensitivity to monoclonal antibody therapeutics

20. Member of the clinical site study team and/or his/her immediate family

21. Pregnant or breastfeeding women

22. Women of childbearing potential\* who are unwilling to practice highly effective contraception prior to the initial dose/start of the first treatment and for the duration of the study. Highly effective contraceptive measures include stable use of combined (estrogen and progestogen containing) hormonal contraception (oral, intravaginal, transdermal) or progestogen-only hormonal contraception (oral, injectable, implantable) associated with inhibition of ovulation initiated 2 or more menstrual cycles prior to screening; intrauterine device (IUD); intrauterine hormone releasing system (IUS); bilateral tubal ligation; vasectomized partner; and or sexual abstinence\*\*.

\*Postmenopausal women must be amenorrheic for at least 12 months in order not to be considered of childbearing potential. Pregnancy testing and contraception are not required for women with documented hysterectomy or oophorectomy.

\*\*Sexual abstinence is considered a highly effective method only if defined as refraining from heterosexual intercourse during the entire period of risk associated with the study treatments.

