**Table 1: Definition of the patient status regarding hepatitis C virus**

Hepatitis C Antibody test result					
	Negative		Positive		
Reflexive test a – hepatitis C RNA test	Not available or HCV RNA not detected	HCV RNA detected	HCV RNA not detected b	HCV RNA detected	Not available
Hepatitis C status – label	Negative	Positive RNA	Negative b	Positive RNA	Positive Ab – no RNA available

a test performed at the same time or after the antibody test in pre-treatment period (for baseline evaluation), or post-baseline, respectively

b For post-baseline evaluation, a second antibody test with a different type of assay is to be done at the same date or after the first antibody test. The result of this test will modify the final hepatitis C status of the patient in some cases (see details in the text below the table)

The baseline evaluation will be based on tests performed during the pre-treatment period.

In case of multiple hepatitis C tests available for the post-baseline evaluation, the positive status of the patient will be defined as follows:

- “Positive RNA” status if at least 1 post-baseline positive RNA is detected, regardless of status of the patient at the end of treatment.
- Else “Positive Ab – no RNA available” status if no post-baseline reflexive RNA test is available for at least 1 post-baseline positive antibody test.

If no antibody test is available or with “indeterminate” as result pre-treatment or post-baseline respectively, the RNA test (if available) will be used alone to determine the status of the patient. If no RNA test is available then the hepatitis C status of the patient will be missing.

The post-baseline status “confirmed positive antibody with negative RNA” will replace “Negative” status as defined above in the case where no RNA was detected post-baseline and the 2 antibody tests surrounding the same visit (from 2 different types of assay) are positive.

For a conservative approach, the post-baseline status “Positive Ab – no RNA available” will not be modified by the availability of a second antibody test from a different assay.

For the description of the positive hepatitis C virus test during the TEAE period, all above rules will apply while replacing post-baseline by TEAE period.

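### SAP 5.7.2 counts an eligible patient with unchanged antibody-positive, RNA-negative hepatitis C results as a seroconversion whenever the second post-baseline antibody assay is positive

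*SAP*

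**What the plan says.** **Definition of the event.** SAP 5.7.2 (Hepatitis C antibody): "Post-baseline seroconversion is defined for patients with a negative baseline status who had either a" positive-RNA status, or the status for confirmed antibody with RNA negative, after baseline. Situations other than these are left to individual evaluation.

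**Status labels.** Table 1 in SAP 5.7.2 applies the same labels at baseline and after baseline. A positive antibody test with no RNA detected is labelled *Negative*, with footnote b attached. The footnote reads: "For post-baseline evaluation, a second antibody test with a different type of assay is to be done at the same date" as the first antibody test, or later.

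**Relabelling.** The text below the table replaces *Negative* by the confirmed-antibody status under this condition: "where no RNA was detected post-baseline and the 2 antibody tests surrounding the same visit (from 2 different types of assay) are positive". It presents this as a post-baseline status. The baseline evaluation uses pre-treatment tests and has neither a second assay nor a confirmed-antibody status.

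**Eligibility.** In Protocol 6.2.2, exclusion 18, the hepatitis C part removes a patient for "Hepatitis C antibody (associated with a positive HCV RNA polymerase chain reaction) at the screening visit". Antibody without detectable RNA does not exclude.

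**Purpose.** Protocol 10.4.4.2 promises the number and percentage of patients with an observed seroconversion, by treatment group, in both study periods. The Amendment 2 rationale says the end-of-period antibody tests were added to look for seroconversion.

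**The concern.** Seroconversion is a change from not having the antibody to having it. Here the baseline side of the comparison is in effect an RNA definition: antibody-positive patients without RNA count as *Negative*. The post-baseline side can be met on antibody alone. A patient who carried the antibody before the first dose can therefore meet the definition with no change in either result. At stake is whether this one safety summary reports what the tests were added to measure. In arms of this size, a single misclassified patient would be visible in the percentages.

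**Working it through.** The documents state no figure for this rule, so there is none to reproduce. The check is to apply the rules as written to every patient whose antibody and RNA results are the same before and after treatment, and see who is counted.

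**Inputs**
- Labels, footnote b and relabelling: SAP 5.7.2, Table 1 and the text below it.
- Event: baseline *Negative*, plus positive RNA or confirmed antibody after baseline (SAP 5.7.2).
- Eligibility: Protocol 6.2.2, exclusion 18.
- Size: about 74 patients, 2:1 (Protocol 5.1).

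**Unchanged-result patients**

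| Antibody | RNA | Passes the hepatitis C part of exclusion 18? | Baseline label | Second assay after baseline | Post-baseline label | Counted? |
|---|---|---|---|---|---|---|
| neg | not detected | yes | Negative | – | Negative | no |
| neg | not available | yes | Negative | – | Negative | no |
| neg | detected | yes | Positive RNA | – | Positive RNA | no |
| pos | not detected | yes | Negative | positive | Confirmed antibody, RNA negative | **yes** |
| pos | not detected | yes | Negative | negative or not done | Negative | no |
| pos | detected | no | Positive RNA | – | Positive RNA | no |
| pos | not available | yes | Positive antibody, no RNA | – | Positive antibody, no RNA | no |

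Exactly one unchanged pattern is counted, and eligibility allows it. It depends on the second assay being positive.

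**Size of one such patient**
- Arms: 74 × 2/3 = 49.3, about 49; 74 × 1/3 = 24.7, about 25.
- Alirocumab: 1/49 = 2.0%. Placebo: 1/25 = 4.0%.

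These percentages take the whole arm as denominator; a smaller denominator would raise them.

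**Open-label period.** SAP 5.7.2 reuses the double-blind summaries, and the general safety rules in SAP 5.7 keep the pre-treatment baseline, so the same patient could appear there too. That depends on a week 24 antibody result. Protocol Table 1 schedules one, but SAP 4.7.2 lists this test only at weeks -2 and 12.

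**Check of the fix.** If the antibody route requires a negative baseline antibody test, the one counted row drops out and no unchanged patient is an event. Patients who go from antibody-negative to confirmed antibody, or to detectable RNA, are still counted.

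**The case against.** **The second assay is a filter.** This stands as a condition. If the second test is negative or not done, the label stays *Negative* and nobody is counted. It does not remove the problem: a second assay guards against a false-positive antibody result, but it cannot tell an old antibody from a new one.

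**The case-by-case sentence covers it.** It does not. That sentence is for situations outside the definition, and this patient is inside it. A program written to the SAP would count the patient.

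**The consequence is small.** This stands. Safety output is descriptive, with no inferential testing (Protocol 10.4.4, SAP 5.7). Hepatitis C is not among the adverse events of special interest. Antibody present before randomisation is unrelated to assignment in expectation, and the error adds events without hiding true ones. Baseline hepatitis C antibody is among the baseline variables (SAP 4.1) summarised under SAP 5.1, so an alert reader could trace an odd event back to it. The protocol's term, observed seroconversion, also suggests a slip in SAP wording and not an intended method.

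**A stronger reading to avoid.** A reader might infer that a false event is likely, or that it would be most of what the table shows. The documents do not support either. They give no antibody prevalence and no expected number of true conversions. If the prevalence of antibody-positive, RNA-negative patients were assumed to be 0.5%, 1% or 2%, then 1 − (1 − p)^74 gives 31%, 52% or 78%. That is the chance of enrolling at least one such patient, under an assumption. It is not the chance of a false event, which also needs a post-baseline sample and a positive second assay.

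**Conclusion.** The point holds, conditionally and narrowly. As written, SAP 5.7.2 classifies an eligible patient who is antibody-positive and RNA-negative at screening, and unchanged afterwards, as a seroconversion if the second assay is positive. This is a stated rule that gives a wrong answer for that patient, not a missing detail. Each such patient adds about 2.0 percentage points (alirocumab) or 4.0 (placebo) to one descriptive safety table, assuming arms of about 49 and 25 with everyone in the denominator. The number of such patients is unknown and may be zero. No efficacy endpoint, test or error rate is affected. It is worth correcting because the correction is small.

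**What to change.** In SAP 5.7.2:

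1. Count the confirmed-antibody, RNA-negative route as seroconversion only for patients with a negative antibody test at baseline.
2. Give patients who are antibody-positive with RNA not detected at baseline their own status in Table 1. List them separately, and report any later detectable RNA in them separately.
3. For the antibody route, send patients whose baseline antibody is missing or indeterminate to the existing case-by-case listing. The SAP now classifies them on RNA alone, so they can be *Negative* at baseline, and item 1 by itself would leave them unassigned.

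The cost is SAP wording and one derivation rule. The baseline antibody result is already collected at screening, so no new test and no protocol amendment are needed. SAP section 1 allows revision before the first-step database lock.

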**Table 1: Definition of the patient status regarding hepatitis C virus**

Hepatitis C Antibody test result					
	Negative		Positive		
Reflexive test a – hepatitis C RNA test	Not available or HCV RNA not detected	HCV RNA detected	HCV RNA not detected b	HCV RNA detected	Not available
Hepatitis C status – label	Negative	Positive RNA	Negative b	Positive RNA	Positive Ab – no RNA available

a test performed at the same time or after the antibody test in pre-treatment period (for baseline evaluation), or post-baseline, respectively

b For post-baseline evaluation, a second antibody test with a different type of assay is to be done at the same date or after the first antibody test. The result of this test will modify the final hepatitis C status of the patient in some cases (see details in the text below the table)

The baseline evaluation will be based on tests performed during the pre-treatment period.

In case of multiple hepatitis C tests available for the post-baseline evaluation, the positive status of the patient will be defined as follows:

- “Positive RNA” status if at least 1 post-baseline positive RNA is detected, regardless of status of the patient at the end of treatment.
- Else “Positive Ab – no RNA available” status if no post-baseline reflexive RNA test is available for at least 1 post-baseline positive antibody test.

If no antibody test is available or with “indeterminate” as result pre-treatment or post-baseline respectively, the RNA test (if available) will be used alone to determine the status of the patient. If no RNA test is available then the hepatitis C status of the patient will be missing.

The post-baseline status “confirmed positive antibody with negative RNA” will replace “Negative” status as defined above in the case where no RNA was detected post-baseline and the 2 antibody tests surrounding the same visit (from 2 different types of assay) are positive.

For a conservative approach, the post-baseline status “Positive Ab – no RNA available” will not be modified by the availability of a second antibody test from a different assay.

For the description of the positive hepatitis C virus test during the TEAE period, all above rules will apply while replacing post-baseline by TEAE period.

### ***Drug-induced liver injury***

The liver function tests, namely AST, ALT, ALP, and total bilirubin, are used to assess possible drug-induced liver toxicity. The proportion of patients with PCSA values or ALT increase as defined as AESI (see [Section 4.7.1.2](#)) during TEAE period by baseline status will be displayed by treatment group for each parameter.

An evaluation of drug-induced serious hepatotoxicity (eDISH) with the graph of distribution of peak values of ALT versus peak values of total bilirubin will also be presented using post-baseline values during TEAE period. Note that the ALT and total bilirubin values are presented on a logarithmic scale. The graph will be divided into 4 quadrants with a vertical line corresponding to 3 x ULN for ALT and a horizontal line corresponding to 2 x ULN for total bilirubin.

Listing of possible Hy's law cases identified by treatment group (i.e., patients with any elevated ALT $>3$  x ULN, and associated with an increase in bilirubin  $>2$  x ULN, concomitantly or not) with ALT, AST, ALP, total bilirubin, and if available direct and indirect bilirubin will be provided.

The incidence of liver-related TEAEs will be summarized by treatment group. The selection of PTs will be based on SMQ Hepatic disorder (see [Section 4.7.1.2](#)).

#### ***Analysis of Clinical Laboratory Variables in Open-Label Period***

For open-label period clinical laboratory parameters, summary tables as described for the double-blind period will be used.

#### **5.7.3. Analysis of Vital Sign Variables**

The vital sign actual values and change from baseline values obtained while sitting will be descriptively summarized at baseline and each post-baseline visit (collected up to the day of last dose of study treatment +21 days) by at least patient number, mean, median, Q1, Q3, SD, minimum and maximum for each treatment group. Additionally, vital sign measures for last on-treatment value and worst on-treatment value will be summarized in a similar manner. Vital sign mean changes from baseline, with the corresponding SE, can be plotted at each visit by treatment group, in the case results warrant further investigation.

Individual patient vital sign measurements (regardless of sitting position) will be additionally evaluated by PCSA criteria, specifically identifying patients with at least one post-baseline measurement that meets the PCSA criteria within the TEAE period. Patients meeting the PCSA criteria at least once will be summarized by patient count (and percent) and treatment group. Patient listings of vital sign measurements that meet PCSA criteria will be provided for the report appendix.

#### ***Analysis of Vital Sign Variables in Open-Label Period***

For open-label period vital sign parameters, summary tables as described for the double-blind period will be used.

#### 5.7.4. Analysis of Electrocardiogram Variables

ECG parameters will be described through an overall interpretation of ECG status. The count and percentage of patients with at least 1 abnormal post-baseline ECG during the TEAE period will be summarized by treatment group according to the following baseline status categories:

- Normal/missing;
- Abnormal

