#### 4.2.3. Safety Endpoints

- Safety parameters (AEs, laboratory data, vital signs, and electrocardiogram [ECG]) assessed throughout the study.

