#### 8.2.4.3. Electrocardiogram

Electrocardiogram should be performed before blood is drawn during the visits requiring blood draws. A standard 12-lead ECG will be performed with the patient in the supine position after resting quietly for 10 minutes at time points according to [Table 1](#). Heart rate will be recorded from the ventricular rate and the PR, QRS, RR and QT intervals will be recorded. The ECG strips or reports will be retained with the source.

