#### **4.7.4. Electrocardiogram Variables**

Electrocardiograms were recorded automatically by the device at the Investigator site at week -2, week 12/or end of double-blind treatment visit, and week 24/or end of open-label treatment visit. Electrocardiogram assessments will be described as normal or abnormal.

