HR	$\leq 50$ bpm and decrease from baseline $\geq 20$ bpm $\geq 120$ bpm and increase from baseline $\geq 20$ bpm	To be applied for all positions (including missing) except STANDING.
SBP	$\leq 95$ mmHg and decrease from baseline $\geq 20$ mmHg $\geq 160$ mmHg and increase from baseline $\geq 20$ mmHg	To be applied for all positions (including missing) except STANDING.
DBP	$\leq 45$ mmHg and decrease from baseline $\geq 10$ mmHg $\geq 110$ mmHg and increase from baseline $\geq 10$ mmHg	To be applied for all positions (including missing) except STANDING.
Orthostatic Hypotension		
Orthostatic SDB		
Orthostatic DBP	$\leq -20$ mmHg $\leq -10$ mmHg	
Weight	$\geq 5\%$ increase from baseline $\geq 5\%$ decrease from baseline	FDA Feb 2007.
ECG		
		Ref.: CPMP 1997 guideline.
HR	$\leq 50$ bpm and decrease from baseline $\geq 20$ bpm $\geq 120$ bpm and increase from baseline $\geq 20$ bpm	
PR	$\geq 220$ ms and increase from baseline $\geq 20$ ms	
QRS	$\geq 120$ ms	

Parameter	PCSA	Comments
QTc	Absolute values (ms)	To be applied to any kind of QT correction formula.
Borderline		
Prolonged*	Borderline: 431-450 ms (Male); 451-470 ms (Female)	
Additional	Prolonged: >450 ms (Male); >470 ms (Female) ≥500 ms	*QTc prolonged and $\Delta$ QTc>60 ms are the PCSA to be identified in individual subjects/patients listings.
	Increase from baseline	
	Borderline: Increase from baseline 30-60 ms	
	Prolonged: Increase from baseline >60 ms	

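### The planned ECG table keeps only normal/abnormal, so it cannot show an interval shift that leaves the reading unchanged or worsening from an abnormal baseline, and no SAP section applies the ECG criteria in Appendix 10.3

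*SAP*

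**What the plan says.** - **Endpoint.** Protocol 4.2.3 names ECG among the safety endpoints: "Safety parameters (AEs, laboratory data, vital signs, and electrocardiogram [ECG]) assessed throughout the study".
- **Collection.** Protocol 8.2.4.3 specifies a 12-lead ECG: "Heart rate will be recorded from the ventricular rate and the PR, QRS, RR and QT intervals will be recorded". Strips or reports stay with the source. The schedule of events (Protocol Table 1) places ECGs at screening, Week 12 and Week 24.
- **Variable.** SAP 4.7.4: "Electrocardiogram assessments will be described as normal or abnormal".
- **Analysis.** SAP 5.7.4: "ECG parameters will be described through an overall interpretation of ECG status". It plans one summary: "The count and percentage of patients with at least 1 abnormal post-baseline ECG during the TEAE period will be summarized by treatment group", in two baseline rows, normal or missing, and abnormal.
- **Criteria.** SAP Appendix 10.3 has ECG rows for heart rate, PR, QRS and QTc. The QTc row has absolute bands by sex, a category from 500 ms upward, and bands for change, including "Prolonged: Increase from baseline >60 ms". A footnote says that prolonged QTc and a rise above 60 ms are the "PCSA to be identified in individual subjects/patients listings".
- **Scope of the criteria.** The common rules in SAP 5.7 define PCSA for laboratory tests and vital signs. ECG is not named.

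**The concern.** The protocol requires the intervals and the SAP's appendix says how to judge them, yet the ECG analysis section reduces each tracing to one label. Laboratory data (SAP 5.7.2) and vital signs (SAP 5.7.3) each get values, changes from baseline, PCSA counts and patient listings. ECG gets none of these, and the SAP gives no reason.

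What is at stake is the descriptive safety record in a small population. The amendment history says alirocumab had not previously been studied in HoFH and gives that as the reason for lengthening the treatment-emergent period. Protocol sections 1 and 3.2.1 describe premature cardiovascular disease in HoFH, so some abnormal baseline ECGs are plausible, although the documents give no rate. Those are the patients for whom the planned table says least.

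**Working it through.** The plan states no figure to reproduce. The check sets the sections side by side and then applies the appendix thresholds to hypothetical patients.

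**Step 1: what each data type receives.**

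| Output | Laboratory (SAP 5.7.2) | Vital signs (SAP 5.7.3) | ECG (SAP 5.7.4) |
|---|---|---|---|
| Values by visit | yes | yes | no |
| Change from baseline | yes | yes | no |
| PCSA counts | yes | yes | no |
| Listing of PCSA values | yes | yes | no |
| Normal/abnormal by baseline status | not applicable | not applicable | yes |

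**Step 2: does another section apply the ECG criteria?** SAP 5.7 limits PCSA to laboratory tests and vital signs. SAP 6.6 has ECG in its list of data types whose unscheduled measurements may contribute to abnormal values and PCSA, but it defines no output. Protocol 10.4.4.2 covers laboratory data and vital signs only. So no analysis section carries out the ECG rows of Appendix 10.3 or the listing its footnote asks for.

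**Step 3: a shift that leaves the reading unchanged.** Take a woman whose QTc goes from 385 to 450 ms.
- Change: 450 − 385 = 65 ms, above the 60 ms criterion.
- Level: 450 ms is below the female borderline band, 451 to 470 ms.
- Result: her overall reading could stay normal, and the table would then not count her.

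In whole milliseconds, a woman can rise by 61 ms and still be below the borderline band if her baseline is at most 450 − 61 = 389 ms. For a man, whose borderline band starts at 431 ms, the limit is 430 − 61 = 369 ms. This shows that the case can arise under the SAP's own thresholds, not how often it would.

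**Step 4: worsening from an abnormal baseline.** Take a man whose QTc goes from 455 to 505 ms, with the baseline ECG read as abnormal.
- Change: 505 − 455 = 50 ms, in the 30 to 60 ms borderline band for change.
- Level: he moves from prolonged (above 450 ms for men) into the category from 500 ms upward.
- Result: he falls in the same cell, abnormal then abnormal, as a man who stays at 455 ms. The table cannot separate the two.

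**Step 5: what the table does show.** A patient who moves from a normal to an abnormal reading is counted, but not attributed to any interval. Missing baselines share a row with normal ones, so an abnormal follow-up after a missing baseline looks the same as a new abnormality.

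**Step 6: inputs for QTc.** The protocol records QT and RR; the criteria are for QTc. The appendix says its QTc criteria apply under any correction formula, and neither document chooses one. QTc can be derived from the recorded values once a formula is stated.

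**The case against.** **No protocol analysis is broken.** The protocol's statistical section specifies no ECG analysis, and SAP 4.7.4 and 5.7.4 agree with each other. This stands. A reader might infer a departure from the protocol, but the documents support only a gap and an unreconciled appendix within the SAP.

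**The appendix is partly a generic list.** SAP 5.7 describes it as a sponsor version dated January 2009. It also holds lipase, amylase and orthostatic blood pressure, which the protocol does not list as assessments. The ECG rows may simply be unused, and a sentence saying so would remove the inconsistency. This stands as an explanation. It would not restore what the table loses, since the protocol does require the intervals.

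**Other routes exist.** A reader might infer that a patient meeting the QTc criterion would appear nowhere in the report. That goes too far. Under Protocol 9.4.5 an ECG finding is reported as an adverse event if it brings symptoms, needs further testing or intervention, or leads to a change in dosing, discontinuation or other therapy. The appendix footnote also calls for the listing, and SAP 5.7.4 omits it without forbidding it. The limitation is confined to the planned ECG table.

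**Heart rate is already covered.** SAP 5.7.3 summarises it with the vital signs, so ECG heart rate adds little to the descriptive tables.

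**No cardiac conduction concern is stated.** The list of adverse events of special interest (Protocol 9.3.3) contains none, and Protocol 3.2.2 describes a favourable safety profile. This stands and keeps the point minor.

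**Conclusion.** The point holds for the planned ECG table. Followed as written, SAP 5.7.4 cannot show an interval change that leaves the overall reading unchanged, nor separate worsening from persistence in patients abnormal at baseline. It can also miss a patient who meets the SAP's own criterion of a QTc rise above 60 ms. The appendix footnote and the analysis section need to be reconciled.

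It is a low-cost improvement to safety reporting. The primary analysis, alpha and power are untouched. A reader might want the lost sensitivity as a percentage, but the documents give no interval means or standard deviations and plan no inferential safety testing, so any such figure would rest on invented inputs.

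The conclusion assumes that the normal/abnormal label reflects the overall reading and not the appendix thresholds. SAP 4.7.4 says the device at the site recorded the ECG automatically, but not who or what assigns the label.

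**What to change.** In SAP 5.7.4, keep the normal/abnormal table and add:

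1. Descriptive statistics of value and change from baseline for PR, QRS, QT and QTc at Week 12 by treatment group, and at Week 24 overall and by double-blind group, as SAP 5.7 already presents open-label data. State the correction formula, and derive QTc from the recorded QT and RR.
2. Counts of patients meeting the Appendix 10.3 ECG criteria, by treatment group and baseline status.
3. The patient listing of prolonged QTc and QTc rise above 60 ms that the appendix calls for.

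In SAP 5.7, extend the PCSA rule to ECG. If the sponsor decides not to use the ECG rows, the SAP should at least say so and why.

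Cost: SAP wording and a few descriptive outputs, with no new procedure. If the intervals are held only on reports at the sites, they must be entered for at most three scheduled ECGs per patient, about 3 × 74 = 222 tracings. Only Week 12 gives a randomised comparison, because all patients receive alirocumab afterwards.
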